3.6.2 Contraindications for use and off-label use

Prevalence of contraindicated or off-label use will be examined according to calendar time, where events marking relevant scientific publications and regulatory decisions will be marked. We will

report the number and proportion of patients prescribed rosiglitazone who had a diagnosis consistent with a contraindication for rosiglitazone use or with off-label use as defined in the Methods. We will provide the proportions in each country and over time. We will follow the analytic methods described above, provided that the sample size is large enough. At a minimum, use by patients with the additional contraindications (ischemic heart disease and/or peripheral vascular disease) listed in the 2008 press release¹⁰ will be examined in the periods before and after the publication of the press release including any prior diagnosis of liver disease, ischemic heart disease, cardiac failure, or acute coronary syndrome.

3.6.3 Acute drug reactions

For patient-level endpoints, baseline will be defined as the recorded date of medication switch/addition (as reflected by a new dispensation/issue); date of the first-time prescription dispensation/issue (in first-time users) or 1 January 2000 (in prevalent users).

We will examine the number of potential drug reactions occurring within 45 days of baseline and calculate the 45-day cumulative incidence of acute drug reactions, overall and diagnosis-specific (if the data set is large enough); We will estimate risk ratios for the acute drug reactions identified using regression, while adjusting for confounding.

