3.6 Analysis plan

3.6.1 Drug utilization patterns

Based on the dates of rosiglitazone marketing, publications, and regulatory decisions, the following four broad periods can be identified, in which drug utilization patterns will be examined, starting with 1 July 2000, when rosiglitazone was introduced to the EU market:

- | | |
|----------|---|
| Period 1 | 1 July 2000 to 23 May 2007 (meta-analysis & by EMA's press release) |
| Period 2 | 24 May 2007 to 24 January 2008 (EMA adds contra-indications) |
| Period 3 | 25 January 2008 to 22 September 2010 (EMA suspends rosiglitazone) |
| Period 4 | 23 September 2010 until data closing date. |

We will evaluate prescribing patterns within these periods and according to calendar month by several methods. First, we will calculate (separately in Denmark and in the UK):

- The number of persons receiving prescriptions for rosiglitazone in each time period, overall and per month during the time period;
- The number of prescriptions for rosiglitazone in each time period, overall and per month during the time period;
- The number of persons receiving a prescription for any specific antidiabetic medication in each time period, overall and per month during the time period;

- The proportion of persons receiving a prescription for any specific antidiabetic medication who received a prescription for rosiglitazone in each time period.

We will describe switching patterns in several ways within each database. First we will determine the proportion of patients on anti-diabetic therapies other than rosiglitazone who switched to rosiglitazone in each of the 4 time periods. We will also describe the proportion of people, by time period, who switched from rosiglitazone to another anti-diabetic medication or who discontinued use of any anti-diabetic medication. Proportions of patients discontinuing rosiglitazone preparations will be determined among those who originally switched to rosiglitazone and among those for whom the rosiglitazone-containing product was the first-ever anti-diabetic prescription. Switching will be defined as 1) stopping all rosiglitazone prescriptions and starting a different anti-diabetic medication, 2) stopping all anti-diabetic medications or 3) adding new anti-diabetic therapies to the current rosiglitazone therapy (concomitant therapies). A person will be considered a switcher once they have received at least 2 prescriptions for a new therapy.

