To more clearly display time trends and the influence of the milestones that separate the time periods, we will create smoothed plots of the four parameters listed in the bullets above. We will define a window of length four months, and calculate each of the four parameters in that window, beginning in the first four months of 2000 (January, February, March, and April). We will plot the values of the four parameters at the midpoint of the window (1 March 2000). We will then slide the window one month forward and recalculate all four parameters in that window (February, March, April, and May of 2000). Data from January of 2000 falls out of the window and data from May of 2000 enters the window). We will plot the values of the four points at the midpoint of the window (1 April 2000). We will continue to slide the four-month window along the time axis until the end of the study period, calculating the parameters and plotting them at the midpoint of each window. The result will be a smoothed plot of trends in the parameters. We expect, for example, that the number of prescriptions for rosiglitazone will not exceed 0 until the first window that includes August 2000 appears. The number of prescriptions for rosiglitazone will likely increase, then reach a steady state, then decrease with the first milestone (May 2007). We will depict these milestone events on the graph, which will clearly display the correspondence between changes in the parameters and the milestone events.

This method of smoothing the results depicts trends without imposing a model on the data. A model embeds assumptions, such as the expected changes in trends at the milestones, which can become a self-fulfilling prophecy. It is important to begin the analysis without a model. If the smoothed data suggest that models of these results would be productive, and the modelling results would be useful, then we will fit models of the appropriate form. We expect these models will require regression splines, with knots (nodes) at the milestone dates. Such models would allow us to calculate, for example, the rate of change in number of prescriptions or proportion of diabetics receiving prescriptions within time periods. The model would also allow a quantitative comparison of the change in proportion in Denmark versus the UK, as a measure of homogeneity of the response in Europe to the milestone events.

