3.6.4 Glycaemic control and other biochemical disease parameters

We will compare recorded plasma glucose concentration, HbA1c values, and other objective disease parameters before and after the baseline. Because the date of dispensation/issue does not precisely indicate the exact date of patient medication switch, we do not know the precise day that the patient starts the new medication), it will be important to explore different time windows after the recorded dispensation/issue date. We will compare measurements at various time points before and after the baseline. The latest measurement before the baseline will be assumed to indicate the baseline value for the analysis. The follow-up time after baseline is expected to vary depending on the date of available laboratory testing. We will conduct analyses examining 1, 3, and 6-month post-baseline changes in laboratory parameters.

Furthermore, we will examine the potential role of secular trends – scientific or media publications and EMA warnings – by controlling in the analysis for time elapsed from an event that could potentially trigger medication switch and the time of actual switch (approximated by the date of the new prescription). We propose that recency of potential triggering events may be an indirect indicator of patient's underlying risk of potential adverse events as perceived by patients themselves or their providers.

4 Quality assurance, feasibility and reporting

This study will be carried out by scientists employed at academic institutions. The study in Denmark will be conducted by the study coordinator, the Department of Clinical Epidemiology (DCE), Aarhus University, Denmark. The study in the UK will be conducted by the Boston Collaborative Drug Surveillance Program (BCDSP), which is an independent research unit affiliated with Boston University, USA. The study was commissioned to the Department of Clinical Epidemiology by the European Medicines Agency. EMA is the sole sponsor of the study. Because

EMA required that data from at least two EU Member States be included in this evaluation, DCE subcontracted BCDSP to conduct the analyses in the United Kingdom.

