6.1 Denmark

The Aarhus University Prescription Database records all reimbursed prescriptions dispensed in community pharmacies of the North and Central Denmark Regions – 2 of the 5 Danish regions, with combined population of 1.8 million, or 30% of the entire Denmark's population. Prescriptions for oral glucose-lowering medications are eligible for general reimbursement and are therefore recorded in this database; more than 98% of antidiabetic prescriptions are dispensed in the primary sector,² and are therefore expected to be recorded in this database. Recorded information includes the Anatomical Therapeutic Chemical classification of the drug, date of the dispensation, and unique product number.

Laboratory Information Systems for North and Central Denmark Regions (LABKA) track all hospital-performed laboratory tests, including those sent to hospital laboratories by general practice. The following data are recorded: the test name and IUPAC-code, the result, the measurement unit, the dates of ordering and carrying each test. The current coverage period for the Central Region ~ October 1999 to September of 2009, inclusive, for the North Region from 1997 to 2008, inclusive.

The Danish Central Personal Registry covers the entire Danish population and since 1968 has registered all births, deaths, and migration of Danish residents. This database contains dates of all recorded events and is updated daily.

The Danish Registry of Causes of Death contains information on causes of death, including associated diagnoses. Data have been collected since 1970.

The Danish National Registry of Patients covers the entire Danish population and has registered hospitalizations since 1977, including outpatient visits since 1995. Up to 20 discharge diagnoses are recorded for each hospital contact, using the International Classification of Diseases 10th revision (ICD-10) since 1994 and ICD-8 in the earlier period.

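### Prevalent users who never switch or add a drug are anchored at 1 January 2000, so their named outcome windows close before any rosiglitazone prescription is expected

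*Protocol*

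**What the plan says.** Section 3.6.3 sets one baseline rule for all patient-level endpoints. It has three branches. The first applies to anyone who changes treatment: "baseline will be defined as the recorded date of medication switch/addition (as reflected by a new dispensation/issue"). The other two are "date of the first-time prescription dispensation/issue (in first-time users) or 1 January 2000 (in prevalent users"). Section 3.4.5 refers the reader to the analysis plan for the meaning of baseline, so the rule in 3.6.3 also governs the laboratory analyses in 3.6.4.

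Two sets of outcome windows run from that baseline. For acute reactions, section 3.6.3 states: "We will examine the number of potential drug reactions occurring within 45 days of baseline". For laboratory parameters, section 3.6.4 states: "We will conduct analyses examining 1, 3, and 6-month post-baseline changes in laboratory parameters". The laboratory windows are not fully closed, because 3.6.4 adds that "it will be important to explore different time windows after the recorded dispensation/issue date" and gives no lengths for these.

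On the drug's arrival, section 3.6.1 divides the calendar into periods "starting with 1 July 2000, when rosiglitazone was introduced to the EU market". The same section expects that "the number of prescriptions for rosiglitazone will not exceed 0 until the first window that includes August 2000 appears".

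Section 3.4.3 defines an acute drug reaction as a first-onset event in the 45 days following a switch to or from rosiglitazone. Section 3.6.3 plans adjusted risk ratios and does not name the reference group.

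**The concern.** A fixed calendar date is a natural start for a description of drug use, and section 3.1 gives that reason for including time before approval. It is a poor time zero for a reaction to a change of treatment. Nothing changed for these patients on 1 January 2000, and by the protocol's own dates none of them could then have been using rosiglitazone as a marketed drug.

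Two things are at stake. First, the 45-day cumulative incidence would include events that follow no switch, which the endpoint definition in 3.4.3 excludes. Second, section 3.3 makes users of other oral drugs an analysis category, and 3.4.5 examines laboratory changes by pattern of use. If continuing users enter such a contrast through their 1 January 2000 windows, outcomes from the first half of 2000 are set against outcomes from August 2000 onwards. Exposure and calendar period then cannot be told apart between those two groups.

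**Working it through.** The protocol gives no figure of its own on this point, so the check is calendar arithmetic followed by a comparison of sections.

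Inputs: baseline 1 January 2000 (3.6.3); windows of 45 days (3.6.3) and 1, 3 and 6 months (3.6.4); market introduction 1 July 2000 and first expected rosiglitazone prescription August 2000 (both 3.6.1).

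Formula: window end = baseline + window length; gap = 1 July 2000 − window end.

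- 45 days: 1 January + 45 days = 15 February 2000; gap 137 days.
- 1 month: 1 February 2000; gap 151 days.
- 3 months: 1 April 2000; gap 91 days.
- 6 months: 1 July 2000; gap 0 days (31 + 29 + 31 + 30 + 31 + 30 = 182 days from baseline).

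Sensitivity to how six months is counted: 180 days ends on 29 June and 183 days ends on 2 July, one day after introduction. From 1 July to 1 August is 31 days, so under any of these conventions the longest named window closes about a month before rosiglitazone prescriptions are expected.

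Who this covers: the switch/addition branch is not limited to first-time users. A patient already treated on 1 January 2000 who switches on, say, 1 June 2007 has a 45-day window ending on 16 July 2007, which is concurrent with rosiglitazone use. The zero overlap therefore belongs to prevalent users with no later switch or addition, and to the named windows.

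Section 3.4.3 against 3.6.3: the former requires a switch to or from rosiglitazone. The latter counts potential reactions within 45 days of baseline, and its baseline includes a date with no switch. Events from 1 January to 15 February 2000 fail the first and are counted under the second.

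Secular-trend control: section 3.6.4 adjusts for the time between a triggering event and the actual switch. These users have no switch, so the quantity is undefined for them. The first milestone, 23 May 2007, also comes almost seven years after their last named window closes (1 July 2000 to 23 May 2007 is 6 years and nearly 11 months).

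**The case against.** The strongest reply is that the patients who matter most are unaffected. The last two specific aims concern switchers, and the first branch of the baseline sentence gives every switcher or adder a later baseline. This stands. A reader might infer that all prevalent users, and every window they contribute, lie before market introduction; the sentence read whole does not support that.

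Second, the protocol names no reference group, and that choice may properly sit in a statistical analysis plan. First-time users of other drugs supply windows across the study period and could serve. This also stands: the non-concurrent comparison is a consequence if these users are employed that way, not something the protocol announces. For the same reason it goes too far to say that no calendar adjustment could help. In a common model, first-time users of other drugs would allow a calendar effect to be estimated. The adjustment fails in a two-group contrast with these users alone.

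Third, section 3.6.4 compares values before and after baseline within patients, so a difference in level between calendar periods does not carry over in full to the laboratory results. That is fair. It weakens the laboratory side but does not make these windows concurrent.

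Fourth, it might be said that 3.4.3 already excludes non-switchers from the acute-reaction count. It does by definition, but 3.6.3 then counts from a baseline that 3.4.3 does not recognise. The two sections have to be reconciled; one cannot be assumed to override the other.

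A reader might also point to the short laboratory look-back, since "The current coverage period for the Central Region ~ October 1999 to September of 2009, inclusive" leaves about three months before 1 January 2000. This concerns one Danish region only. Section 6.1 gives the North Region from 1997, and section 3.1 has the UK database collecting data since 1987. It adds little.

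**Conclusion.** The point holds in a limited form. For prevalent users without a later switch or addition, calendar overlap between the named windows and expected rosiglitazone use is zero. That result needs only the protocol's own dates and survives any ordinary way of counting six months. Two consequences follow: the 45-day count as written admits events that do not meet the endpoint definition, and these users cannot be a concurrent reference. The first holds whichever reference group is chosen; the second matters only if they are used in a contrast.

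It is tempting to convert this into a stated distortion of the risk ratio from falling cardiovascular rates, season and a typical switch date. The document gives none of these inputs, and the calculation would also require a reference made up wholly of 1 January 2000 windows. No figure for the bias should be quoted. The number of patients affected is not given either.

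The change should be made because the date is fixed in the protocol and the repair is cheap. It does not undermine the analyses of switchers.

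**What to change.** Delete the 1 January 2000 baseline from section 3.6.3, which also removes it from 3.6.4. Restrict acute-reaction windows to actual switches, additions or first prescriptions. Bring 3.4.3 and 3.6.3 into line: 3.4.3 now admits only switches to or from rosiglitazone, so state there whether additions and first prescriptions count as well.

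Prevalent users would then enter the patient-level analyses at a later switch or addition, as the first branch of the rule already allows. 1 January 2000 can remain the start of the utilisation analyses in 3.6.1.

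If continuing users are wanted as a reference, assign each an index date in the same calendar month as the rosiglitazone switch with which they are compared.

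The cost is a short rewording of two sections and some programming of index dates on existing records. The windows lost carry no usable information on rosiglitazone or on switching.

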The present study was commissioned by the European Medicines Agency (EMA), following the suspension of rosiglitazone preparations in the European Union. EMA wishes to retrospectively examine the impact of risk minimisation actions in the European Union (such as warnings, scientific publications, and regulatory decisions) on utilization of rosiglitazone and on the condition of rosiglitazone-using patients with type 2 diabetes (the target population).

2 Specific aims

The specific aims of this study are as follows:

- To describe trends in patterns of utilisation of rosiglitazone-containing preparations over time, in particular, in response to external events, such as scientific and media publications, EMA's press releases, or EMA's regulatory decisions aimed at risk minimisation;
- To examine the extent of use of rosiglitazone-containing preparations in persons with potential contraindications;
- To examine the extent of use of rosiglitazone-containing preparations in persons outside the primary indication (off-label use);
- To examine risk of acute drug reactions among patients who switch from alternative antidiabetic therapies to rosiglitazone preparations or vice versa;
- To examine glycaemic control and other objective parameters of disease among patients who switch from alternative antidiabetic therapies to rosiglitazone preparations or vice versa.

3 Methods

3.1 *Setting and study population*

This study will be conducted in Denmark and in the United Kingdom (UK).

In Denmark, the source population includes residents of the country's North and the Central regions, with combined population of about 1.8 million, or approximately 33% of the population. Denmark is a welfare state, with universal, tax-funded access to all medical services, including reimbursement for prescribed medicine. Many medical services rendered in Denmark have been routinely and prospectively recorded, on patient level, for the past several decades in population registries; data linked from these registries will be used in the present study.¹⁴

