In the UK, the study will be conducted based on data from the General Practice Research Database (GPRD). The GPRD is an ongoing longitudinal database that collects data from over 350 general practices in the UK since 1987. The UK provides a unique medical environment to create a computerized medical data resource for medical epidemiological research for two main reasons: a) the primary health care system comprehensively covers the UK population; b) the information on all relevant medical care is located in the offices of the general practitioners (GPs), who function as "gatekeepers" for hospital and specialist referrals in the UK health system. The GPRD contains information on more than 6 million patients, of whom 3.5 million are currently registered, and a

cumulative follow-up time of more than 40 million person-years. It covers 6% of the UK population; this sample is representative with respect to age, gender and race/ethnicity distribution.

The study population will include, in both countries, diabetic patients treated with oral glucose lowering drugs between 1 January 2000 and 1 January 2011. This period covers the time from the approval of rosiglitazone for use in the European Union, in July 2000, until the decision by the European Medicines Agency to suspend the drug, on 23 September 2010. The study period also includes a pre-approval and a post-suspension periods to allow examination of drug utilization patterns in response to these events.

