3.4.3 Acute drug reactions

Both acute and pre-existing events will be identified in the Danish National Registry of Patients and in the Registry of Causes of Death in Denmark and in the GPRD's Event file, in the UK.

Acute drug reactions will be defined as new (first-onset) events occurring 45 days after the date of the switch to or from a rosiglitazone preparation. We will use prior hospitalization records to screen out prevalent/prior events and conditions. The exact distribution of events that may represent a potential acute drug reaction is unknown until data analysis. We will rank all recorded new events in the order of seriousness and potential of representing an acute drug reaction. Since cardiovascular side effects are a major safety concern for rosiglitazone, as a minimum, we will examine the following events:

- All-cause mortality;
- Cardiovascular mortality;
- Acute myocardial infarction;
- Cerebrovascular accident/ischemic stroke
- Pulmonary embolism;
- Deep vein thrombosis.

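### Prevalent users get a 45-day acute-reaction window starting 1 January 2000, when no treatment changed and rosiglitazone was not yet marketed, which conflicts with the protocol's own definition of an acute drug reaction

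*Protocol*

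**What the plan says.** The fourth aim in section 2 of the protocol is "To examine risk of acute drug reactions among patients who switch from alternative antidiabetic therapies to rosiglitazone preparations or vice versa". Section 3.4.3 follows this aim and defines acute drug reactions as "new (first-onset) events occurring 45 days after the date of the switch to or from a rosiglitazone preparation".

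Section 3.6.3, the analysis text for the same endpoint, is wider. For patient-level endpoints, "baseline will be defined as the recorded date of medication switch/addition (as reflected by a new dispensation/issue"), or as the date of the first prescription in first-time users, "or 1 January 2000 (in prevalent users"). It continues: "We will examine the number of potential drug reactions occurring within 45 days of baseline", with a 45-day cumulative incidence, and then "We will estimate risk ratios for the acute drug reactions identified using regression, while adjusting for confounding". No sentence removes prevalent users from these steps, and no reference group is named.

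Section 3.1 places the "approval of rosiglitazone for use in the European Union, in July 2000". Section 3.6.1 starts its first utilisation period on 1 July 2000, as the date of market introduction, and expects no rosiglitazone prescriptions before August 2000.

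**The concern.** A short risk window for acute reactions means something only if it opens at a change in exposure. For switchers, adders and new starters, the baseline in section 3.6.3 is such a change. For prevalent users it is the first day of the study period. They were already taking their drug before that day and continued to take it afterwards.

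Two things are at stake. First, if the rule is followed as written, events that occur in early 2000 among established users of other drugs are counted as potential acute reactions, although they are background events. Second, risk ratios are promised without a named reference. An analyst could take the prevalent-user windows as the unexposed group. Those windows would then differ from the rosiglitazone switch windows in calendar time and in how long patients had already been on therapy.

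**Working it through.** The protocol gives no figure to reproduce on this point. The check is date arithmetic, followed by a comparison of the two sections.

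**Inputs from the protocol**
- Prevalent-user baseline: 1 January 2000 (section 3.6.3).
- Risk window: 45 days (section 3.6.3).
- Market introduction of rosiglitazone: 1 July 2000 (section 3.6.1).
- First rosiglitazone prescriptions expected: August 2000 (section 3.6.1).
- Last day before suspension: 22 September 2010 (section 3.6.1).
- Study period: 1 January 2000 to 1 January 2011 (section 3.1).

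**Dates**
1. End of window = 1 January 2000 + 45 days = 15 February 2000.
2. Gap to market introduction = 15 February to 1 July 2000 = 14 (rest of February, a leap year) + 31 + 30 + 31 + 30 + 1 = 137 days.
3. Gap to the first expected prescriptions = 137 + 31 = 168 days, to 1 August 2000.
4. Overlap of the window with rosiglitazone availability = 0 days.
5. Share of the study period covered = 45 / 4,018 days = 1.1%, all of it in early 2000.
6. Switches to rosiglitazone before suspension can occur from 1 July 2000 (0.5 years after the prevalent-user baseline) to 22 September 2010 (10.7 years after it).

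**The two sections side by side**

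| | Section 3.4.3 (endpoint) | Section 3.6.3 (analysis) |
|---|---|---|
| Clock starts at | a switch to or from rosiglitazone | a switch or addition, a first prescription, or 1 January 2000 |
| Prevalent user on 1 January 2000 | no qualifying date | has a baseline and a 45-day window |
| Event on, say, 1 February 2000 | not an acute drug reaction | a potential drug reaction within 45 days of baseline |

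Because rosiglitazone was not on the market, no patient can have switched to or from it by 15 February 2000. Every event in these windows therefore fails the endpoint definition. The conflict is complete for this group and not a matter of degree.

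**Direction of bias if these windows were the reference**
- Calendar time: any secular fall in cardiovascular risk would make the early-2000 reference risk higher than that of later switchers and push the ratio down.
- Season: all the windows lie in January and February, while switches can fall in any month.
- Established therapy: these patients have already tolerated and survived their drug, which tends to lower the reference risk and push the ratio up.
- Entry rule: section 3.3 requires two or more prescriptions within the study period. A prevalent user who dies before the second never enters, which lowers observed 45-day mortality in this group. Switchers face a similar two-prescription rule, so the net effect on a ratio is unclear.

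These forces do not all act in the same direction, and the protocol gives no size for any of them.

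**The case against.** The strongest reply is that the baseline sentence is generic. It opens by referring to patient-level endpoints, section 3.4.5 sends the reader to the analysis plan for the meaning of baseline, and section 3.6.4 uses baseline for the laboratory comparisons. The 1 January 2000 clause may be meant for those analyses. A prevalent user who switches later gets a switch-date baseline for that switch, and section 3.4.3 already limits what counts as a reaction. All of this is fair, and it confines the defect to windows actually anchored on 1 January 2000. It does not remove the defect: the clause stands under the acute-reaction heading, the next paragraph counts events from that baseline, and nothing says which section prevails.

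Three stronger readings are tempting, and the document supports none of them.
- A reader might infer that prevalent users are pooled with switchers because section 3.6.3 speaks of overall incidence. In that sentence *overall* is contrasted with *diagnosis-specific*, so it means all event types together, not all patient groups. Section 3.3 sorts users into separate categories.
- A reader might infer that prevalent users are the comparator. Section 3.6.3 names no reference group, and first-time users, adders and other switchers all have a proper starting date. Leaving the choice to an analysis plan is not in itself an error.
- A reader might put a number on the bias by assuming an annual decline in cardiovascular risk and an average switch date. The protocol gives neither, it does promise adjustment for confounding, and prior tolerance of therapy acts against the calendar effect.

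**Conclusion.** The point holds in a narrow form. As written, section 3.6.3 opens a 45-day acute-reaction window for prevalent users at a date with no treatment change. The window closes 137 days before rosiglitazone was marketed. Its events cannot satisfy section 3.4.3 or inform the fourth aim, so the two sections contradict each other for this group.

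The certain part rests only on the protocol's dates and definitions: 0 days of overlap, and no event in these windows that qualifies. The rest is conditional. If the windows enter the 45-day incidence, they add background events. If they serve as reference for the risk ratios, they have no calendar overlap with rosiglitazone switches, so adjustment for calendar time could only extrapolate, and they consist of patients already established on therapy. The net direction of that bias is unknown, and no size should be stated.

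**What to change.** 1. In section 3.6.3, state that the 1 January 2000 baseline does not apply to the 45-day acute-reaction analysis. It may stay for other patient-level endpoints if it is needed there.
2. Include prevalent users in the 45-day analysis only from a dated switch, addition or start.
3. Reconcile sections 3.4.3 and 3.6.3 so that both use the same list of qualifying dates. Section 3.4.3 now recognises only switches to or from rosiglitazone, so its wording must also allow the same 45-day count in the reference group.
4. Take the reference for the risk ratios from patients with a dated non-rosiglitazone start, switch or addition, and adjust for calendar time.

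The cost is protocol wording and a change to the cohort query in a study of existing records. The downside is a smaller group for the 45-day analysis, but the windows given up contain no treatment change and so carry no information on reactions to one.
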